Title: Brain and Gut Plasticity in mild TBI or post-acute COVID Syndrome Following Growth Hormone Therapy

Principal Investigator: [name]., Internal Medicine, UTMB

Co-I: [name]., Internal Medicine, UTMB

Co-I: [name]., Pediatrics, UTMB

Co-I: E. [name]., Internal Medicine, UTMB

Institution: The University of Texas Medical Branch at Galveston

Sponsors: The Moody Endowment

Sealy & Smith Foundation

Specific Aims

Increasing evidence suggests the gastrointestinal (GI) microbiome is altered in patients with history of mild traumatic brain injury (mTBI). In this project, we propose to characterize the GI microbiome in patients with a history of mTBI or post-acute COVID syndrome complex (PASC) in comparison to healthy controls. Furthermore, we propose to investigate the potential effects of recombinant Human Growth Hormone (rhGH, given as somatropin, a polypeptide hormone (GENOTROPIN)) on the GI microbiome, fatigue, cognition, brain activation, and brain morphology in individuals with a history of mTBI or PASC.

Specific Aim 1a. To characterize the GI microbiome in patients with a history of mTBI compared to controls. - mTBI Baseline vs. Control Baseline - Fecal samples for determination of the GI microbiome will be collected monthly from mTBI subjects and healthy controls over 6 months to examine the diversity of the microbiome within and between groups. **Outcomes:** Genus, species, q-PCR for selected marker organisms.

Specific Aim 1b. To characterize the GI microbiome in patients with a history of mTBI based on presence of *Prevotella spp.* - mTBI *Prevotella spp.* positive Baseline vs. mTBI *Prevotella spp.* negative Baseline - Fecal samples for determination of the GI microbiome will be collected monthly from mTBI subjects over 6 months to examine the diversity of the microbiome within and between groups. **Outcomes:** Genus, species, q-PCR for selected marker organisms

Specific Aim 2. To characterize the GI microbiome in patients with a history of post- COVID-19 syndrome (PASC) compared to arm 2 controls. - PASC Baseline vs. Control Baseline - Fecal samples for determination of the GI microbiome will be collected monthly from PASC subjects over 6 months to examine the diversity of the microbiome within and between groups. **Outcomes:** Genus, species, q-PCR for selected marker organisms.

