analysis of the GI microbiome will be collected monthly for the duration of the study. Insulin Growth Factor 1 (IGF-1) levels will be monitored at a month 1 safety visit for all PASC subjects. The month 1 safety visit will occur +/- 5 days from the expected date based on the baseline study visit. The fecal sampling will occur +/- 7 days from the expected date based on the baseline study visit at months 0, 1, 2, 3, 4, 5, 6, 9 and 12. The month 6 study will occur +/- 7 days from the expected date based on the baseline study visit. The month 9 study will consist of fecal sample and questionnaires only. At month 12, the subject will return to the ITS-CRC to repeat the glucagon stimulation test (GST). Questionnaires and a fecal sample will also be collected at this time. A member of the study team will contact the subject each month to coordinate fecal sample transport to UTMB, check for adverse events and overall well-being, and ensure compliance and ongoing consent. If a PASC subject is infected with COVID again during the study months 9 - 12, the study will be extended to collect fecal samples and questionnaires for an additional 3 months.

Therapeutic Intervention (for mTBI subjects only - Arms 1&2; PASC subjects – Arm 3). Recombinant human growth hormone (rhGH), (GENOTROPIN). Growth hormone (GH) is produced endogenously by the body and is released by the pituitary. Therapeutic rhGH is FDA approved for clinical use for replacement of endogenous growth hormone in children and adults with growth hormone deficiency. GENOTROPIN, the agent to be used in this study is manufactured by Pfizer Inc and contains somatropin, which is a polypeptide hormone of recombinant DNA origin. It contains 191 amino acid residues and is identical to human growth hormone of pituitary origin.

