- Montreal Cognitive Assessment (MoCA). The Montreal Cognitive Assessment (MoCA) (20) is a rapid assessment of cognition. The MoCA consists of 9 questions with the following subcategories: visuospatial/executive, naming, memory, language, abstraction, delayed recall and orientation. The MoCA has been used extensively to detect cognitive impairment in many conditions, including head trauma. Version 7.1 will be used at the Month 0 testing and Version 7.2 will be used at the Month 6 testing.

GI microbiome. The GI microbiome will be assessed using fecal samples collected at monthly time points (baseline (month 0), month 1, month 2, month 3, month 4, month 5, and month 6). Additional fecal samples will be collected for Arm 3 PASC subjects at month 9 and month 12. If a mTBI subject sustains an additional TBI during the study period, the study will be extended to collect fecal samples for an additional 6 months. If a PASC subject is infected with COVID again during the study months 9 - 12, the study will be extended to collect an additional sample at month 13 and month 15. Subjects will provide fecal samples as described below. Fecal samples will be collected +/- 7 days from specified time point based on baseline (month 0) study. Subjects will be allowed to collect monthly fecal samples at home. Samples will be stored at 4°C until transferred to UTMB (on/+ 3 days after collection). Subjects will be given a tutorial on how to properly collect the fecal sample. They will be given a handout from the manufacturer of the collection kit with step by step instructions. They will also be shown a video of the collection process supplied by the kit manufacturer. https://www.youtube.com/watch?v=ytr_hmJdHqM&feature=youtu.be&rel=0

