Up to 15 ml of blood (1 serum separator top (5ml); 1 lithium heparin (6ml); 1 K-EDTA (4ml)) will be collected from fasted (at least 10 hours) subjects for analysis of hormones, amino acids and metabolites. In addition, up to 13ml of blood (1 serum separator top (5ml); 1 lithium heparin (6ml)) will be collected after a standardized meal for the analysis of amino acids.
An additional 20ml of blood will be collected for the following labs to be sent to the UTMB clinical laboratory for analysis (labs sent to UTMB lab will be entered into subjects UTMB medical chart):
 - Complete blood count with differential (CBC w/ diff)
 - Comprehensive metabolic panel (CMP)
 - Lipid Panel
- Amino Acid Levels. Circulating blood amino acid levels will be measured before (fasting) and 90 minutes (+/-10 minutes) after a standardized meal. Amino acids in response to a meal will be measured at month 0 and month 6.
- GI microbiome. The GI microbiome will be assessed using fecal samples collected at monthly time points (month 0, month 1, month 2, month 3, month 4, month 5, and month 6). Subjects will provide fecal samples as described above (see procedures for mTBI subjects – GI microbiome). Fecal samples will be collected +/- 7 days from specified time point based on baseline (month 0) study. Subjects will be allowed to collect the fecal samples at home. Samples will be stored at 4°C until transferred to UTMB (on/+ 3 days after collection). Subjects will be given a tutorial on how to properly collect the fecal sample. They will be given a handout from the manufacturer of the collection kit with step by step instructions. They will also be shown a video of the collection process supplied by the kit manufacturer.

https://www.youtube.com/watch?v=ytr_hmJdHqM&feature=youtu.be&rel=0

An additional collection will be performed at month 0 and month 6 to collect viable fecal material. Fecal samples will be collected using the spatula included in the OMNIgene-Gut kit used in the first collection. Briefly, after the participant transfers fecal material to the yellow top of the collection

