- Gastrointestinal Symptom questionnaire. Gastrointestinal symptoms will be monitored monthly using the Gastrointestinal Symptom Rating Scale (GSRS). The GSRS is a 15-item questionnaire. Each question has a seven-point Likert-type scale where 1 represents absence of symptoms and 7 represents very troublesome symptoms. The GSRS will be measured monthly.

For Arm 1 only: If the mTBI subject sustains an additional TBI during the study period, the study will be extended for both the mTBI and household control for an additional 6 months. The GSRS will be collected monthly during the 6 month extension.

○

Statistical Considerations

Aim 1a:

In this protocol we intend to compare the GI microbiome of diagnosed mTBI patients against the microbiome of healthy controls (HC). Data will be organized by time (PRE vs. POST) and by treatment (mTBI vs. HC). The hypothesis is that group differences between mTBI and HC will exist at PRE but that GH treatment in the mTBI group will dissolve these differences at POST.

Power calculations using q-PCR data from 22 diagnosed TBI patients and 15 healthy control subjects suggesting that we will be able to detect group differences in genus and/or species in the intestinal flora. These calculations suggest that we would need about 6 subjects per group to have an 80% probability of detecting significant differences in at least one of the previously

identified organisms (two-sided, $\alpha=0.05$). With the proposed subject numbers (25 per group) we calculate that the power would be between 91 – 100 % for at least 8 of the previously identified organisms.

Aim 1b:

Given our recent results from mTBI patients with BIAFAC, that identified two distinct community groups, based upon the presence of specific *Prevotella* species, we require additional participants to achieve group sizes of each type to address differences in the individual species for the pre and post comparisons. Enrollment: We expect to enroll subjects without the need for a HHC to address these differences. These subjects will be compared to matched normal participants from the general population adding 25 TBI and 25 normals to the study creating the power needed to address *Prevotella* positive and negative community types.

[figure not shown]
Aim 2:

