Given the data acquired from two PASC subjects under IRB 20-0361 that have shown indistinguishable profiles to those of BIAFAC communities as well as remarkably reduced GH responses to GST, we expect that the Power calculations explained in this section (above) will also apply to PASC. Because PASC is a recent consequence to the pandemic no data exist to complete Power calculations beyond those of syndromes like BIAFAC that present with similar symptoms. We therefore have proposed enrollment of at least 25 PASC subjects to compare to 25 normal controls already included in this protocol.

For quantifiable (primary) outcomes such as abundances of individual species in the GI microbiome and (secondary) symptom related outcomes, a standard repeated measure ANOVA model will be used. When possible, age and other covariates will be brought into the model to reduce variability and account for random differences between the two groups. Significance tests will be performed at the $\alpha=0.05$ level, and multiple testing corrections will be used to account for potential Type I error rate inflation. Nonparametric, generalized linear, and transformed response models will be considered as necessary to alter the model to account for deviations from standard assumptions (normality, linearity, etc.). Current data support statistical outcomes being established with group sizes similar or slightly larger size than our previous study.

The graph below is based on group difference in *Alistipes onderdonkii*. Power calculations were performed using t-tests with G*Power (two-groups, two-sided, $\alpha=0.05$, Version 3.1.9.2, Germany). Effect size in this case was 1.184.

Below is a list of organisms we identified previously and which were used to conduct the power analyses for the present study. Please note that the intestinal flora includes an incredibly diverse system of organisms and at this time it is difficult to accurately predict which organisms will be included in the biome shifts we expect to see. Therefore, additional organisms may be included in the final microbiome comparisons between mTBI patients and household control subjects. Further power analyses will be conducted using the data collected during this investigation.

Target	n = 20 (10/group)	n=30	n=40	n= 50 (25/group)
Alistipes onderdonkii	70.7%	87.9%	95.4%	98.4%
Desulfovibrio	60.4%	79.3%	89.9%	95.4%
Prevotella spp	97.5%	99.8%	100.0%	100.0%
Akkermansia	64.8%	83.2%	92.6%	96.9%

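### The stool samples from months 1 to 5 enter no stated analysis; define PRE and POST and fit a mixed model to all monthly samples, keeping month 6 minus month 0 as the main contrast

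*Combined protocol and SAP*

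**What the plan says.** Under Statistical Considerations, Aim 1a, the protocol states: "Data will be organized by time (PRE vs. POST) and by treatment (mTBI vs. HC". The general model paragraph under Aim 2 adds that for species abundances and symptom outcomes "a standard repeated measure ANOVA model will be used". Neither place says which months PRE and POST are, or how many time levels the ANOVA has.

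The sampling is denser than that layout. mTBI subjects give "fecal samples collected at monthly time points (baseline (month 0), month 1, month 2, month 3, month 4, month 5, and month 6" (Study Procedures, GI microbiome), and controls give "fecal samples collected at monthly time points (month 0, month 1, month 2, month 3, month 4, month 5, and month 6" (Study Procedures for household and healthy control subjects). GSRS is completed on the same monthly schedule. PASC subjects follow a longer schedule, "based on the baseline study visit at months 0, 1, 2, 3, 4, 5, 6, 9 and 12", which makes nine stools.

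Specific Aim 1a gives the series a purpose: samples are "collected monthly from mTBI subjects and healthy controls over 6 months to examine the diversity of the microbiome within and between groups". The contrast named for that aim is "mTBI Baseline vs. Control Baseline". Specific Aim 3 compares month 0 with month 6, and the study procedures label the month-6 visit as the post visit.

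**The concern.** The hypothesis in Statistical Considerations, Aim 1a, is that group differences present at PRE disappear at POST after growth hormone. That is a group-by-time question. The plan collects seven time points per mTBI subject and control but states an analysis with two. The five intermediate stools serve a stated purpose that no stated model, summary or test carries out.

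Two things are at stake:

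- **Incomplete subjects.** With two time levels, the group-by-time test is a comparison of change scores. A subject without the PRE or POST stool has no change score and is lost, even if five or six other samples exist.
- **Freedom of choice.** With PRE and POST undefined, the intermediate samples could be brought in, pooled or ignored after the data are seen.

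**Working it through.** **1. The plan's own figure.** A two-sided, two-sample t-test at alpha 0.05 with effect size 1.184 (*Alistipes onderdonkii*) has noncentral-t power of 70.7%, 87.9%, 95.4% and 98.4% at 10, 15, 20 and 25 per group. This matches the table. It is power for a group comparison at one time point; the documents give none for group-by-time.

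**2. The month-6 contrast.** With complete data and month as a factor crossed with group, the mixed-model estimate of (month 6 minus month 0) equals the difference in cell means, as in the PRE/POST ANOVA. The gain therefore comes mainly from incomplete subjects. The protocol expects about 4 Arm 1 pairs to drop out while 25 complete: 4/(25 + 4) = 14% of pairs. Their stools would inform a mixed model but not the two-level ANOVA.

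**3. The supporting contrast.** Let sigma² be the variance of one stool value, rho the within-subject correlation, and k the number of POST months averaged. Under compound symmetry:

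Var(change) = sigma²(1 − rho)(1 + 1/k)

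Relative to k = 1, the ratio is (1 + 1/k)/2, whatever rho is:

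- k = 3 (months 4 to 6): (1 + 1/3)/2 = 0.667, a 33% cut
- k = 6 (months 1 to 6): (1 + 1/6)/2 = 0.583, a 42% cut

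Under AR(1), the months 4 to 6 ratio is 0.74, 0.78, 0.80 and 0.78 at rho 0.3, 0.5, 0.7 and 0.9, a cut of about 20 to 26%.

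**4. From variance to power.** Lower variance helps only if the averaged months carry the effect. Assumed example: 25 v 25 independent subjects, a shift of 0.7 sigma at month 6, rho 0.6, compound symmetry. The SDs of change in units of sigma are √0.800 = 0.894, √0.533 = 0.730 and √0.467 = 0.683.

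| Time course of effect | Month 6 − month 0 | Months 4–6 − month 0 | Months 1–6 − month 0 |
|---|---|---|---|
| Full from month 1 | 77% | 91% | 94% |
| Linear over months 1–6 | 77% | 79% | 54% |
| Zero to month 3, then linear to month 6 | 77% | 60% | 22% |

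The months 4 to 6 mean carries 5/6 of the month-6 effect in the second row and 2/3 in the third. Under AR(1) with rho 0.6 and linear build-up, power is 42% for month 6 and 38% for months 4 to 6. At 50 v 50, the compound-symmetry month-6 contrast already has 97%.

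**5. The baseline comparison.** mTBI treatment starts at the baseline study, so only the controls have further untreated samples. If each control's seven-sample mean replaces the single value:

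SE ratio = √{[1 + rho + (1 − rho)/7]/2}

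This is 0.84, 0.89 and 0.93 at rho 0.3, 0.5 and 0.7, so the SE is 16%, 11% and 7% smaller. It assumes no time trend in controls.

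**The case against.** A reader might infer that the plan reduces each subject to one PRE and one POST value and discards five of seven stools. The documents do not say so. PRE and POST are undefined in the statistical section, the number of ANOVA levels is open, and Specific Aim 1a gives the monthly samples a purpose. What stands is narrower: no stated analysis uses months 1 to 5. The five-of-seven count also does not apply to PASC subjects, who give nine stools.

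A reader might also infer that averaging late months is worth 1.5 to 1.7 times the subjects. That needs compound symmetry and the full effect in every averaged month. The protocol gives no time course, and it plans a dose step after the month-1 check, so an immediate full effect cannot be presumed.

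Making a late-months average the main contrast would also move the estimand away from month 6. Specific Aim 3 names month 6, and in mTBI subjects MoCA, BFI and MFSI are measured only at months 0 and 6. That objection stands, so month 6 should remain the main contrast.

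Three further points limit the size. The protocol enrols extra Arm 1 pairs so that 25 complete, and gives no rate of missed endpoint stools, so the loss from incomplete subjects cannot be quantified. The Enrollment section plans 50 mTBI subjects and 50 controls across Arms 1 and 2, which leaves less to gain than 25 v 25. Eight listed organisms already have 91 to 100% stated power, although that is for one time point.

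None of this supplies the missing analysis. If PRE and POST mean months 0 and 6, the intermediate stools have no stated use; if they mean something else, the time factor is unspecified.

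**Conclusion.** The point holds as a gap in the analysis specification that should be closed. PRE versus POST in a standard repeated-measures ANOVA is the only stated layout, months 1 to 5 enter no stated test, and a subject missing an endpoint stool is lost from a two-level ANOVA.

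The benefit of a longitudinal model is real but conditional. For the month-6 contrast it is mainly the retention of incomplete subjects, of unknown size, and it relies on data being missing at random. For a months 4 to 6 contrast the variance falls by 33% (compound symmetry) or about 20 to 26% (AR(1)), with a useful gain in power only if the effect is largely in place by month 4. For the baseline comparison the gain is on the control side only, about 7 to 16% in SE for rho from 0.7 to 0.3. The correlation, the time course and the 0.7 sigma shift are assumptions. The stated power figures need no correction on this point.

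**What to change.** In Statistical Considerations:

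- Define PRE as month 0 and POST as month 6.
- For stool outcomes and GSRS, replace the two-level ANOVA with a linear mixed model on all monthly samples: group, month as a factor, group-by-month, a stated within-subject correlation structure, and a suitable transform.
- Name group-by-(month 6 minus month 0) as the main one-degree-of-freedom contrast.
- Pre-specify group-by-(mean of months 4 to 6 minus month 0) as a supporting contrast, reported beside it.
- For the baseline comparison, add a sensitivity version that uses all untreated control samples.

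No visit, sample or subject is added. The cost is slightly more analysis work and one extra reported contrast.

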Notably, the cluster of symptoms associated with post-COVID syndrome include profound fatigue and cognitive dysfunction, which are strikingly consistent with BIAFAC. While studies are underway to understand the details of the mechanism causing BIAFAC and why GH treatment alleviates symptoms in these patients, we are intrigued that the symptom phenotype with post-COVID patients overlaps with many BIAFAC symptoms. It is possible that post-COVID syndrome may be addressed through similar treatment strategies including the potential for prebiotic/probiotic enhancement of microbiome health.

Therefore, in the current study we will assess the GI microbiota in individuals with a history of mTBI or PASC and fatigue. Each participant's baseline will serve as an individual control. An additional and critical control dataset that will be used for comparisons will be provided by analysis of the GI microbiome from healthy controls. Furthermore, we will investigate whether treatment with recombinant Human Growth Hormone (rhGH) will create changes in the gut flora producing microbiomes more similar to those expected in healthy controls and whether these changes correlate with the expected improvements in fatigue, cognition, brain activation, and brain morphology in the mTBI or PASC patients.

Experimental Design and Methods

Enrollment

TBI subjects: To address **AIM 1a** and **AIM 1b** we will study subjects with a history of mild TBI enrolled into either **arm 1** (n=25) or **arm 2** (n=25) for a total of (**n=50**).

Healthy Controls: To address **AIM 1** and **AIM 3** we will study healthy control subjects enrolled into either **arm 1** (n=25) or **arm 2** (n=25) for a total of (**n=50**).

[figure not shown]
PASC subjects: To address **AIM 3** we will study subjects with a history of COVID-19 and PASC symptoms enrolled into **arm 3** (**n=25**).

ARM 1: mTBI and Household Controls

Subjects. We will study subjects (aged 18-70 years) with a history of mild TBI (n=25) and their household controls (aged 18 years and up) (n=25). mTBI subjects will undergo a 6-month intervention of rhGH therapy (See Figure 1). Household controls will be asked to participate in questionnaires, blood draws (amino acid analysis), and fecal sampling (GI microbiome analysis). Household controls will not receive any growth hormone treatment.

mTBI group

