All patients presenting with a prior mTBI will undergo a phone pre-screen including the Brief Fatigue Inventory (BFI) questions 1-3. If they score ≥ 3 on any BFI questions 1-3, and are interested in participating in the study, they will be scheduled for a formal consenting and medical screening at the UTMB Clinical Research Center (CRC). During the medical screening, eligibility will be confirmed and a glucagon stimulation test (GST) will be performed. A glucagon stimulation with a growth hormone peak of <10 ng/mL is required to qualify for enrollment. This is the range we have used in our previous studies to be inclusive of all subjects who have a less than normal (>10 ng/mL) response to GST. In our previous studies, patients with a response to the GST in the 3 – 10 ng/mL range have benefited from GH therapy as much as those with a less than 3 ng/mL response.

Household control group

All household controls will undergo a phone pre-screen and if interested in participating in the study, will be scheduled for a formal consenting and medical screening at the UTMB Clinical Research Center (CRC).

[figure not shown]
ARM 2: mTBI and Healthy Matched Controls

Subjects. We will study subjects (aged 18-70 years) with a history of mild TBI (n=25) and healthy age/sex matched controls (aged 18-70 years) (n=25). mTBI subjects will undergo a 6-month intervention of rhGH therapy (See Figure 2). Healthy matched controls will be asked to participate in questionnaires, blood draws (amino acid analysis), and fecal sampling (GI microbiome analysis). Healthy controls will not receive any growth hormone treatment.

Figure 1. ARM 1: Study Design. Patients with a history of mTBI, fatigue of ≥ 3 on the BFI and GH <10 ng/ml will undergo 6 months of GH replacement therapy. Household controls will also be recruited for each mTBI patient. Both mTBI and control subject sets will collect fecal samples and fill out a GI questionnaire (GIQ) monthly over the study period.

mTBI group

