1. If paired household control subject withdraws consent, mTBI subject will be terminated from the study.
2. If subject reports they have missed more than 7 consecutive days of study medication administration, they will be terminated.

Household Control Subjects:

1. If paired mTBI subject withdraws consent or is terminated, household control subject will be terminated from the study.

Subjects enrolled in Arm 2 & 3:

mTBI/PASC Subjects:

1. If subject reports they have missed more than 7 consecutive days of study medication administration, they will be terminated.

Procedures and Time Frames for Communicating Outcomes:

Monitoring Reports will be prepared and forwarded to the IRB on an annual basis.

Precautions for Maintaining Data Integrity:

Careful monitoring of the recruitment, enrollment, retention, adverse events, and study procedures will help to protect the safety of study subjects, the quality of data, and the integrity of the study. As part of the safety plan for this study, the PI will review individual study subject records to ensure that appropriate mechanisms to protect the safety of study participants are being followed, that protocol requirements are being adhered to, and that data is accurate, complete, and secure. Subject records include consent forms, case report forms, flow of data forms, laboratory specimen records, inclusion/exclusion forms, cumulative toxicities and/or adverse event logs, and medical charts.

Records Retention

The investigator shall retain the records for 15 years.

Inclusion of Women and Minorities

Women and men will be included, as GENOTROPIN is approved for both.

Minorities will be included in the proportion found in the general population (see Targeted Enrollment Table)

Targeted/Planned Enrollment Table

Study Title: Brain and Gut Plasticity in mild TBI or post-acute COVID Syndrome Following Growth Hormone Therapy

Total Planned Enrollment: Up to 125 subjects. We would like to complete n=50 TBI subjects (enrolled in arm 1 and arm 2), n=50 control subjects (enrolled in arm 1 and arm 2) and n=25 PASC subjects (arm 3).

Targeted/ Planned Enrollment: Number of Subjects			
Ethnic Category	Sex/Gender		
	Females	Males	Total
Hispanic or Latino	13	12	25
Not Hispanic or Latino	50	50	100
Ethnic Category: Total of All Subjects *	63	62	125
Racial Categories			
American Indian/Alaska Native	0	0	0
Asian	0	0	0
Native Hawaiian or Other Pacific Islander	0	0	0
Black or African American	13	12	25
White	50	50	100

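### The protocol does not settle whether Aim 1a uses Arm 1 alone (25 v 25) or both arms (50 v 50), and the named model fits neither the two control types nor the household pairs

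*Combined protocol and SAP*

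**What the plan says.** **Who is assigned to the aim.** Experimental Design and Methods, Enrollment, assigns mTBI subjects from Arm 1 (25) and Arm 2 (25) to Aims 1a and 1b together. For Aims 1 and 3, "we will study healthy control subjects enrolled into either" of the same two arms, again 25 + 25. The Targeted/Planned Enrollment Table repeats the totals: "n=50 TBI subjects (enrolled in arm 1 and arm 2), n=50 control subjects (enrolled in arm 1 and arm 2").

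**What is powered.** Statistical Considerations, Aim 1a, reads: "With the proposed subject numbers (25 per group) we calculate that the power would be" 91–100% for at least eight organisms. The power table stops at 25 per group. The method is an unpaired two-group t-test, two-sided, alpha 0.05. For *Alistipes onderdonkii*, "Effect size in this case was 1.184".

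**Where the second 25 + 25 enters.** In Statistical Considerations these subjects appear under Aim 1b, to enlarge the *Prevotella* positive and negative community types.

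**Which controls.** Specific Aim 1a and the Aim 1a statistics text say healthy controls. The overall hypothesis in Background and Significance says household controls. The text above the organism list refers to "final microbiome comparisons between mTBI patients and household control subjects". Specific Aim 2, by contrast, names the Arm 2 controls outright.

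**How the controls are built.** Arm 1 has mTBI subjects and "their household controls (aged 18 years and up) (n=25"); Arm 2 has "healthy age/sex matched controls (aged 18-70 years) (n=25").

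**Model.** A repeated-measures ANOVA organised by time (pre, post) and group (mTBI, healthy control). Age and unspecified other covariates may be added when possible. Arm, control type and household pair are not named.

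**The concern.** A reader cannot tell whether 50 or 100 people answer the first aim, or which kind of control they are compared with. If this stays open, the analyst could choose after seeing the data between 25 household pairs, 25 mTBI subjects with matched volunteers, or a pool of both.

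The choice matters because the control sets differ by design. Cohabitants may share diet and environment with the patient, have no upper age limit and are not matched on sex. Arm 2 controls come from the general population, are matched on age and sex, and stop at 70. If the mTBI difference shows against one kind of control only, a single pooled estimate would not reveal it.

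**Working it through.** **1. Reproduce the plan's power.** Inputs from Statistical Considerations: unpaired t-test, two-sided alpha 0.05, d = 1.184 for *Alistipes*, and the 10-per-group column of the table. Power comes from the noncentral t with noncentrality d·√(n/2) and 2n − 2 degrees of freedom.

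- *Alistipes*, n = 25: 1.184 × √12.5 = 4.19, df 48, critical t 2.011, power 98.4%, as printed. At 10, 15 and 20 per group: 70.7, 87.9 and 95.4%, as printed.
- For the other rows d is not printed. Solving it from the 10-per-group column gives 0.956 (Odoribacter) to 1.856 (Prevotella) for the eight best, then 0.688, 0.647 and 0.186. These values reproduce the remaining columns to within about 0.1 point.
- Exactly eight organisms reach 91.2–100% at 25 per group.

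The stated 91–100% is therefore right for an unpaired 25 v 25 comparison.

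**2. The same effect sizes at 50 v 50** (97 degrees of freedom with an arm term). For Odoribacter the noncentrality is 0.956 × √25 = 4.78.

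| Target | 25 v 25 | 50 v 50 |
|---|---|---|
| Odoribacter (lowest of the eight) | 91.2% | 99.7% |
| Sutterella | 91.5% | 99.7% |
| Alistipes onderdonkii | 98.4% | >99.9% |
| Lachnoclostridium | 66.4% | 92.6% |
| Streptococcus salivarius | 61.2% | 89.3% |
| 16s | 9.8% | 15.1% |
| Effect detectable at 80% power | 0.81 SD | 0.57 SD |

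These figures use uncorrected alpha, as the plan's do, although the plan promises multiple-testing correction. If that were Bonferroni over the 11 listed targets (assumed), the eight would have 65.5–100% at 25 v 25 and at least 96.7% at 50 v 50.

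**3. Omitting arm from a pooled model.** With 25 per arm in each group, arm is orthogonal to group, so the average mTBI–control contrast is unbiased with or without it. Only the error term changes. Assume a true effect of 0.5 SD. The estimate has SD √(2/50) = 0.20 and the critical t is about 1.984.

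- Both groups differ by 1 SD between arms (assumed). Without arm, the within-group variance is 1 + 0.5² = 1.25 and the model's standard error is 0.2236. Power ≈ Φ((0.5 − 1.984 × 0.2236)/0.20) = Φ(0.28) = 61%. With arm: Φ((0.5 − 0.397)/0.20) = Φ(0.52) = 70%.
- Only the controls differ by 1 SD (assumed). Without arm, the average variance is 1.125, the standard error 0.2121 and power 65%. With an arm main effect, the variance is 1.0625, the standard error 0.2062 and power 67%.
- Both groups differ by 1 SD but the effect is Odoribacter's 0.956: 99.5% without arm, 99.7% with it.

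**4. Could a group-by-arm test settle whether both control types agree?** The interaction has standard error √(4/25) = 0.40 SD. If the Arm 1 effect were half the Arm 2 effect (assumed), the noncentrality is 0.592/0.40 = 1.48 for *Alistipes* (31% power) and 0.478/0.40 = 1.20 for Odoribacter (22%).

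**5. If Arm 1 stands alone.** For 25 pairs the noncentrality is d·√(25/(2(1 − r))) with 24 degrees of freedom. Odoribacter has 90.0, 95.2 and 98.7% power at within-pair correlations of 0, 0.2 and 0.4 (assumed). If sharing a household also shrank the Arm 1 difference to 0.75 or 0.5 of its size (assumed), an unpaired Arm 1 analysis would have 70.0 or 38.1%. A 50 v 50 pool, with the full effect in Arm 2, would have 98.5 or 94.4%.

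**The case against.** The strongest reply is that the text can be read coherently: Aim 1a is Arm 1, 25 v 25 against household controls, and Arm 2 was added for Aim 1b. The statistics text for Aim 1b and the reference to household controls support this, and on that reading the power fits and an arm term has no meaning. This stands as one reading, and 50 v 50 is not established as the plan. It does not remove the contradiction. The Enrollment section assigns controls from both arms to Aim 1 without separating 1a from 1b, and Specific Aim 1b as worded compares mTBI subjects only with each other. On the Arm 1 reading the named model also ignores the household pairs.

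A second reply is that the mismatch is conservative and that the covariate clause leaves room for arm. The first part is correct. The second is only partly so: the clause is optional, is aimed at random differences between groups, and does not prespecify a structural factor.

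A reader might also infer that omitting arm seriously damages the analysis, citing 61% against 70%. The documents do not support that. The loss needs mTBI subjects as well as controls to differ by 1 SD between arms. Recruitment of mTBI subjects is described in nearly the same terms in both arms, and their eligibility differs only by the household-partner and MRI items. If only the controls differ, the loss is about 2 points, and at the plan's own headline effect sizes it is negligible.

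**Conclusion.** The point holds as an unresolved contradiction about the Aim 1a analysis set, with a model that does not yet suit either choice. Under 50 v 50 it lacks control type and household pairing; under Arm 1 alone it lacks pairing.

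A reader might infer that the stated power suits neither plan, or that the study is too small. Neither follows. The 91–100% is correct for an unpaired 25 v 25 comparison and too low for 50 v 50, where the eight organisms reach at least 99.7%. Nor does pooling without arm bias the average contrast while arm stays balanced. What is lost is some precision and, more importantly, sight of whether the difference holds against both kinds of control.

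These figures assume that the pilot effect sizes carry over to both control types, that alpha is uncorrected, and that 25 per cell complete. The sizes of the arm shifts, the household attenuation and the within-pair correlations are assumptions, since the documents give no values for them.

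**What to change.** State the Aim 1a analysis set in Statistical Considerations and make the Enrollment section, the Aim 1b text and the comparator wording agree with it.

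- **If both arms:** add arm (control type) as a fixed factor. Report the mTBI–control estimate with its interval separately against household and general-population controls. Present any group-by-arm test as descriptive, because its power is low. Account for the Arm 1 household pairs, for example with a household random effect. Restate power at 50 per group at the alpha that will actually be used.
- **If Arm 1 alone:** correct the Enrollment section, keep the 25-per-group basis, and analyse the household pairs as pairs.

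The cost is revised wording, a recomputed power table and one model degree of freedom for arm. No new subjects, visits or samples are needed.
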